3.2 Study Endpoints

3.2.1 Primary Study Endpoints

The primary study endpoint will focus on the decrease in pain of the affected shoulder measured by VAS scores. Based on their responses and their scores at the time prior to and after their barbotage therapy begins, we can determine a primary endpoint with a 10% change between baseline and their final visit. We would also like to observe the affected rotator cuff tendon and measure the efficacy of barbotage therapy via shoulder radiograph. Shoulder X-Ray is considered standard of care and we expect a resolution in size of the calcified deposit by at least 10% after aspiration and lavage.

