5.2.3 Intermediate Visits

Intermediate Visits (Week 6, Month 3)

- Follow-up visits
- Record VAS

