5.2.4 Final Study Visit

Final Study Visit (End of Month 6)

- Record VAS, ASES Shoulder, and QuickDASH scores.
- Perform Shoulder Series X-Ray for Research Purposes

CONFIDENTIAL

This material is the property of the NYU School of Medicine and Langone Medical Center. Do not disclose or use except as authorized in writing by the study sponsor

6 Assessment of Safety

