8.1 Sample Size

We will aim to enroll a total of 140 subjects. According to a post hoc power analysis calculating the effect size using our preliminary data, >128 patients are required with $d=0.6$ to obtain a power of 0.80 and an alpha value of 0.05. Therefore we are including an additional 10 patients per group to account for patients that may be lost to follow up. Statistical analysis will be performed using chi-squared and/or fisher's exact testing depending on size for binary variables. Continuous variables will be compared with paired t-tests if the data is approximately normally distributed. If the data is not normally distributed, Mann-Whitney tests will be used. All protected health information will be removed prior to statistical analysis.

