8.2 Measures to Minimize Bias

8.2.1 Enrollment/Randomization/Masking Procedures

Patients will be randomized (1:1) using REDCap. The physicians and patients will be blinded to their assigned treatment group.

As each patient receives the barbotage, the patient nor the PI will not know if they are receiving the cortisone in addition to the barbotage. Study team members and [name] will not be blinded and in position to randomize the patients. [name] will not be blinded to the study as she is performing the procedures. [name], the PI, and his patients will be blinded from which combination of the two they receive (barbotage and cortisone or saline/sham).

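### Loss to follow-up is met only by extra enrolment, with no analysis set or missing-data method, and withdrawn patients are deleted and replaced, so the month-6 VAS comparison rests on attenders

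*Combined protocol and SAP*

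**What the plan says.** Section 8.1 sets the target ("We will aim to enroll a total of 140 subjects"), states that ">128 patients are required with" an effect size of d = 0.6 "to obtain a power of 0.80 and an alpha value of 0.05", and adds: "Therefore we are including an additional 10 patients per group to account for patients that may be lost to follow up". Allocation is equal: "Patients will be randomized (1:1) using REDCap" (8.2.1). The rest of 8.1, and the statistical line of the Protocol Summary, list tests only. Neither says who is analysed or what happens when a month-6 value is missing.

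Sections 9 and 10 treat missing data as form entries to be explained and queried, not as an analysis question. Section 4.7.2 is the only rule at patient level: a withdrawn patient's data leave the database and another patient is enrolled. It does not say whether someone who simply stops attending counts as withdrawn.

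Under 3.2.1, "we can determine a primary endpoint with a 10% change between baseline and their final visit". Section 5.2.4 lists the "Final Study Visit (End of Month 6"; section 5.2.3 separately lists "Intermediate Visits (Week 6, Month 3". VAS is recorded at all of these visits. Radiographs are taken only at baseline and month 6.

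**The concern.** A larger sample makes up for lost precision. It does nothing about who is missing. If patients with more pain in one arm stop attending, the remaining patients in that arm look better than the arm as randomised, and the comparison shifts in that arm's favour.

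Deleting and replacing withdrawn patients has the same effect and also discards evidence. A patient who withdraws after month 3 has up to two post-treatment VAS scores that would inform the missing month-6 value. Under 4.7.2 those scores go, and the replacement is a different person who did not withdraw.

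Section 8.2.1 leaves study team members unblinded. That is a further reason to settle the handling of missing outcomes before data accrue.

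**Working it through.** **1. The plan's own figures.** Inputs from 8.1: 140 enrolled, more than 128 required, 10 extra per group. From 8.2.1: 1:1, so 70 per arm.
- Losing 10 per group: 20/140 = 14.3%. This leaves 140 − 20 = 120, below the stated requirement.
- Keeping 128: 140 − 128 = 12 losses at most, 12/140 = 8.6%, or 6 per arm.
- 128 plus 20 would be 148, not 140.

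The allowance is therefore 12 to 20 of 140. Separately, 128 does not reproduce at d = 0.6: a two-sided two-sample t-test at power 0.80 and alpha 0.05 needs 90 in total, and 128 corresponds to d = 0.5. That does not decide this point. With 120 evaluable, power is 0.903 at d = 0.6 and 0.775 at d = 0.5.

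**2. Size of the attenders-only bias.** Suppose loss in one arm is unrelated to pain. In the other, a share f is lost, and the lost patients' true month-6 VAS averages δ SD worse than that of the patients who stay. Then

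bias = f × δ, and SE = √(2/n), with n attenders per arm.

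δ is an assumption; the documents give nothing from which to set it.

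| Lost per arm | f | SE (SD units) | δ = 0 | δ = 0.35 | δ = 0.7 | δ = 1.0 |
|---|---|---|---|---|---|---|
| 6 of 70 | 0.086 | √(2/64) = 0.177 | 0 | 0.03 | 0.06 | 0.09 |
| 10 of 70 | 0.143 | √(2/60) = 0.183 | 0 | 0.05 | 0.10 | 0.14 |

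A bias of 0.10 SD is 0.10/0.183 = 0.55 SE. With no true difference, the two-sided rejection rate is then Φ(−1.96 + 0.55) + Φ(−1.96 − 0.55) = 0.079 + 0.006, or about 8.5% instead of 5%.

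**3. Do the visits already scheduled help?** Simulation with assumed inputs: normal VAS; correlation 0.5 among follow-up visits and 0.3 with baseline; 70 per arm; no true difference; on average 10 lost per arm, at random in one arm and by a logistic model on month-3 pain in the other (slope 2 per SD).
- Attenders only: bias 0.10 SD, spread of the estimate 0.181 SD.
- Month-6 VAS predicted within arm from baseline, week-6 and month-3 VAS: bias below 0.01 SD, spread 0.180 SD.
- Across slopes 1 to 2 and follow-up correlations 0.5 to 0.7, the attenders-only bias was 0.06 to 0.14 SD with 10 lost per arm and 0.04 to 0.09 SD with 6 lost.

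The prediction step assumes that loss depends on recorded VAS. If it depends on unrecorded month-6 pain, some bias remains, hence the sensitivity analysis below.

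**4. If the 10% change is analysed as a responder rate.** Take assumed results of 42/60 against 30/60, with 10 missing per arm (uncorrected chi-squared). Attenders only: 70.0% − 50.0% = +20.0 points (p = 0.025). Extreme scorings of the missing run from (52 − 30)/70 = +31.4 points (p = 0.0002) to (42 − 40)/70 = +2.9 points (p = 0.73). With 6 missing per arm (45/64 against 32/64), the extremes are +27.1 points (p = 0.001) and +10.0 points (p = 0.23). These are outer bounds, not expected results.

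**The case against.** The strongest reply is that the harm depends on the scenario. With the same loss mechanism in both arms and no true difference, omitting lost patients creates no spurious contrast. The documents give no ground for expecting uneven loss. That stands: the bias may be zero, and 0.1 SD is an illustration.

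A reader might also infer three stronger points, which the documents do not support.
- *That the endpoint wording in 3.2.1 lets a week-6 or month-3 score stand in for month 6.* Section 5.2.4 places the final study visit at the end of month 6, and 5.2.3 calls the other two intermediate. The wording is at most loose. For radiographs no earlier film exists to substitute.
- *That the plan budgets a settled 14% loss.* The same paragraph's requirement of more than 128 allows only 8.6%.
- *That false positives rise to about 15%.* That figure needs losses of 15 against 5 and lost patients scored as non-responders. The plan states neither, and it also needs an assumed 55% responder rate. The statement in 1.2 that slightly more than half of patients get relief does not refer to a 10% VAS change.

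Finally, multiple imputation is not the only valid method. A repeated-measures model on the scheduled VAS visits would also close the gap.

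**Conclusion.** The concern holds in this form: the protocol anticipates loss of 8.6% to 14.3% of patients, defines no analysis set and no missing-outcome method, and deletes and replaces withdrawals. By default the month-6 VAS test therefore runs on attenders.

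The resulting bias is zero if loss is unrelated to outcome. It is about 0.1 SD, roughly half a standard error, if loss in one arm follows month-3 pain. That rests on assumed correlations and loss mechanisms. The gap in the plan does not rest on those assumptions. It should be corrected, since the VAS data needed for a better analysis are already scheduled.

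**What to change.** - **8.1:** State that all randomised patients are analysed in their assigned arm. Estimate the month-6 VAS contrast with missing values multiply imputed within arm from baseline, week-6 and month-3 VAS, or with an equivalent repeated-measures model. Derive any 10% classification from the imputed score. Do not carry an earlier visit forward. Add one sensitivity analysis that shifts the imputed values in the barbotage-alone arm until the conclusion changes.
- **4.7.2:** Keep data collected before withdrawal where permitted, instead of deleting them. Section 11.4 already lets the investigator use information collected before authorization is revoked. Do not let a replacement patient stand in for a randomised one in the analysis. Without this change the imputation has no records to work from.
- **Radiographic outcome:** Report it on patients with a month-6 film, with the number missing per arm and a sensitivity analysis. Nothing in the documents supports predicting deposit size from the VAS course.
- **8.1, loss allowance:** Reconcile the extra 10 per group with 140 and the requirement of more than 128.
- **3.2.1:** Naming the month-6 visit would be a wording clarification only.

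Cost: protocol wording and a small amount of analysis work, with no new visits. The interval may be slightly wider than in an attenders-only analysis.

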14	CONFLICT OF INTEREST POLICY	15
15	REFERENCES	17
16	ATTACHMENTS	17

CONFIDENTIAL

This material is the property of the NYU School of Medicine and Langone Medical Center. Do not disclose or use except as authorized in writing by the study sponsor

List of Abbreviations

AE	Adverse Event/Adverse Experience
CFR	Code of Federal Regulations
CRF	Case Report Form
CSOC	Clinical Study Oversight Committee
DCC	Data Coordinating Center
DHHS	Department of Health and Human Services
DSMB	Data and Safety Monitoring Board
FFR	Federal Financial Report
FWA	Federalwide Assurance
GCP	Good Clinical Practice
HIPAA	Health Insurance Portability and Accountability Act
ICF	Informed Consent Form
IRB	Institutional Review Board
ISM	Independent Safety Monitor
MOP	Manual of Procedures
N	Number (typically refers to participants)
NIH	National Institutes of Health
OHRP	Office for Human Research Protections
OHSR	Office of Human Subjects Research
PI	Principal Investigator
QA	Quality Assurance
QC	Quality Control
SAE	Serious Adverse Event/Serious Adverse Experience
SOP	Standard Operating Procedure
US	United States

CONFIDENTIAL

This material is the property of the NYU School of Medicine and Langone Medical Center. Do not disclose or use except as authorized in writing by the study sponsor

Protocol Summary

[figure not shown]
Title	Calcific Tendonitis Treatment-Barbotage vs. Barbotage with Cortisone Injection: A Randomized Controlled Double-Blind Study
Short Title	Calcific Tendonitis Treatment-Barbotage vs. Barbotage with Cortisone Injection
Protocol Number	S19-01299
Population	A sample size of 140 patients belonging to NYU Langone Health with calcific tendonitis will be enrolled including both genders, ages 18-90.
Objectives	The purpose of this study is to determine the efficacy of barbotage therapy by comparing the clinical and sonographic changes in patients that solely receive barbotage to patients receiving the standard of care, barbotage with cortisone injection.
Study Center(s)	Single-center, prospective study
Number of Subjects	We will aim to enroll a total of 140 subjects.
Study Duration	The estimated duration of the study is 24 months.
Subject Participation Duration	Each patient will be present for the day of treatment and follow-up at: 6 weeks, 3 months, and 6 months. Patients will be in the study for 6 months.
Estimated Time to Complete Enrollment	The estimated time to completion of enrollment is 24 months.

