Statistical Methodology	Statistical analysis will be performed using ANOVA or t tests. Pearson's correlation will be used to determine relationship between outcomes scores.

CONFIDENTIAL

This material is the property of the NYU School of Medicine and Langone Medical Center. Do not disclose or use except as authorized in writing by the study sponsor

Drug/Device Template Version: 13 JUN 2016

Schematic of Study Design

CONFIDENTIAL

This material is the property of the NYU School of Medicine and Langone Medical Center. Do not disclose or use except as authorized in writing by the study sponsor

1 Introduction, Background Information and Scientific Rationale

1.1 ***Background Information and Relevant Literature***

Calcific tendonitis is a disorder characterized by pain and development of calcium deposits on one or more rotator cuff tendons and affecting normal sleeping habits and routine daily activities. Inflammation associated with the calcium deposit is theorized to contribute to the pain [1]. A few studies state the prevalence of the condition has been reported to be 3 to 10% in the general population [2, 3]. Several treatment modalities exist including anti-inflammatory and analgesic, extra-corporeal shockwave therapy (ESWT), ultrasound-guided needling and lavage (barbotage), and surgical treatment are in use. However, a consensus to which treatment is superior nor most effective does not exist.

1.2 ***Rationale***

Ultrasound-guided barbotage is a safe and efficient form of therapy for calcific tendonitis, with slightly more than half of the patients experiencing pain relief [4]. The procedure involves percutaneous insertion of a needle with saline, washing and aspirating the fluid content of the joint. By irrigating and aspirating the calcium deposit, symptomatic relief is achieved and signs of pathological resolution is seen on sonogram. All of this is achieved while preserving the native tendon, potentially avoiding surgery. Barbotage with cortisone injection continues to be the standard of care for calcific tendonitis resistant to physical therapy and cortisone injection, but it is not known if barbotage alone can provide the same amount of clinical and symptomatic resolution. We would like to evaluate and witness any significant difference from the standard treatment of care.

1.3 ***Potential Risks & Benefits***

1.3.1 ***Known Potential Risks***

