2.1 Primary Objective

The primary objective of the study is to determine the efficacy of barbotage without cortisone on patients with calcific tendonitis by measuring their clinical improvement via VAS, QuickDASH, and ASES Shoulder scores and radiographic size of calcium deposit.

3 Study Design and Endpoints

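### Section 8.1 names a paired t-test for normally distributed continuous outcomes, which does not compare the two independent randomised arms on VAS

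*Combined protocol and SAP*

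**What the plan says.** The analysis rules stand inside section 8.1 (Sample Size). For continuous outcomes: "Continuous variables will be compared with paired t-tests if the data is approximately normally distributed". The next sentence gives the alternative: "If the data is not normally distributed, Mann-Whitney tests will be used". For binary outcomes: "Statistical analysis will be performed using chi-squared and/or fisher's exact testing depending on size for binary variables". None of these sentences names an endpoint, a time point or a contrast. The Statistical Methodology row of the Protocol Summary says only: "Statistical analysis will be performed using ANOVA or t tests".

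The design is a parallel one. Sections 5.1 and 8.2.1 allocate each patient 1:1 to barbotage with saline or barbotage with cortisone. No section describes matching, crossover or use of the other shoulder as a control. The Objectives row of the Protocol Summary gives the purpose as "comparing the clinical and sonographic changes in patients that solely receive barbotage to patients receiving the standard of care, barbotage with cortisone injection". Section 2.1 is worded more like a single-arm aim: "determine the efficacy of barbotage without cortisone on patients with calcific tendonitis by measuring their clinical improvement via VAS". Section 3.2.1 makes the fall in VAS pain the lead primary endpoint and adds: "we can determine a primary endpoint with a 10% change between baseline and their final visit".

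**The concern.** A paired t-test needs two linked measurements on each unit. Patients in different arms are not linked, so the test does not fit the comparison for which the trial was randomised. It can be read in two ways.

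- **Before and after treatment, within each arm.** The wording of sections 2.1 and 3.2.1 makes this plausible. Section 8.1 then has no test of saline against cortisone for normally distributed VAS. Both arms receive barbotage, so improvement within an arm says nothing about whether omitting cortisone matters. The Mann-Whitney fallback compares independent groups, so a normality check would change the question asked and not only the method.
- **Between arms.** The analyst would have to pair unrelated patients, and the p-value could depend on an arbitrary ordering.

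At stake is whether the primary comparison is specified at all for the most natural form of the primary endpoint. If it is not, the test can be chosen after the data are seen.

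**Working it through.** **1. Which test does the sample size fit?** Section 8.1 gives more than 128 patients, d=0.6, and the targets "to obtain a power of 0.80 and an alpha value of 0.05". Sidedness is not stated; I assume two-sided. All figures use the noncentral t distribution.

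| Test | d=0.5 | d=0.6 |
|---|---|---|
| Two-sample t | 63.8, so 64 per arm, total 128 (power 80.1%) | 44.6, so 45 per arm, total 90 (power 80.4%) |
| Paired t | 34 pairs (power 80.8%) | 24 pairs (power 80.4%) |

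The plan's 128 is not reproduced at its stated d=0.6 by either test. It is reproduced exactly by a two-sided two-sample t-test at d=0.5. The number therefore looks like an independent-groups calculation and not the paired test named in the same paragraph.

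**2. Reading as a within-arm test.** Suppose each arm were judged by its own paired test and the two verdicts compared. The plan states no such rule. Let p be the power of a one-sample t-test with n=64 at a standardised change dz. With identical arms, the chance that exactly one is significant is 2p(1−p). The values of dz are assumptions; the documents give none.

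| dz | p | 2p(1−p) |
|---|---|---|
| 0.2 | 0.351 | 0.455 |
| 0.3 | 0.657 | 0.451 |
| 0.4 | 0.883 | 0.206 |
| 0.5 | 0.976 | 0.047 |
| 0.6 | 0.997 | 0.006 |

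Chance disagreement is common only if improvement is modest. Where both arms improve substantially, both tests are significant whether or not the arms differ.

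**3. Reading as a between-arm test with arbitrary pairs.** Simulation: 3,000 data sets, 64 per arm, 200 random pairings each.

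- Type I error: 4.7% paired, 4.9% unpaired.
- Power at d=0.6: 91.7% paired, 92.0% unpaired.
- Share of data sets in which between 5% and 95% of the pairings were significant, so that the verdict turned on the pairing: 17% at d=0.3, 11% at d=0.5, 6% at d=0.6.

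**4. Power of valid replacements.** Take 60 per arm, which is 140/2 − 10, using the allowance of 10 per group in section 8.1. Let d be in units of the 6-month SD, with equal SDs at both visits, and let r be the correlation of baseline with 6-month VAS, assumed 0.3 to 0.5. The effective effect sizes are:

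- 6-month score: d.
- ANCOVA: d/√(1−r²). At d=0.6 this is 0.6/√0.91 = 0.629 for r=0.3 and 0.6/√0.75 = 0.693 for r=0.5.
- Change score: d/√(2(1−r)). At d=0.6 this is 0.6/√1.4 = 0.507 for r=0.3 and 0.6/√1.0 = 0.600 for r=0.5.

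Each is put into the two-sample t power at two-sided alpha 0.05. The one further degree of freedom that ANCOVA uses is ignored.

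| Analysis, 60 per arm | d=0.6 | d=0.5 |
|---|---|---|
| Unpaired t, 6-month score | 90.3% | 77.5% |
| ANCOVA | 92.7–96.4% | 81.3–88.0% |
| Unpaired t, change score | 78.7–90.3% | 63.1–77.5% |

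**The case against.** The strongest reply is that this is a one-word slip. The total of 128 and the Mann-Whitney fallback both belong to independent groups, and writing unpaired restores validity. I accept that as the likeliest explanation, but an analyst who follows section 8.1 literally would still run the wrong test.

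A second reply is that the plan does contain between-arm tests. This is true, and a reader who inferred that it names none would be going too far. Mann-Whitney is one, but only when the data are not normal. Chi-squared and Fisher's exact tests are others, and they would serve VAS if the 10% change in section 3.2.1 were a responder outcome compared between arms; the text does not say that it is. The Protocol Summary's line on ANOVA or t-tests could cover an unpaired t-test. It is an unranked list that names no contrast, so it neither cures section 8.1 nor strictly contradicts it. The defect is thus confined to VAS, and other outcomes, analysed as normally distributed continuous variables.

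A third reply is that the numerical harm is small. This also stands in large part. Arbitrary pairing leaves error rates almost unchanged, and the disagreement rates in step 2 depend on assumed effects and on a decision rule that the plan does not contain. What survives is the argument of principle: a within-arm test does not compare the arms.

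**Conclusion.** The point holds and should be corrected before analysis. For continuous, normally distributed VAS, section 8.1 names a test that does not properly compare the two arms, and no other section designates one that does.

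Two stronger inferences are not supported. The wording does not imply an inflated type I error: on the pairing reading the simulated rate is 4.7%. Nor does it imply that some 45% of trials would mislead: that figure needs identical arms, a standardised change of 0.2 to 0.3 and separate within-arm verdicts, and the documents supply none of these.

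The choice of replacement does matter. With 60 per arm, an unadjusted change score can fall below the 80% target even at the plan's own d=0.6 (78.7% at r=0.3). At d=0.5 only ANCOVA stays above 80%. These powers rest on a two-sided alpha of 0.05, equal SDs at both visits, d in 6-month SD units and r of 0.3 to 0.5, none of which the documents state apart from the alpha level. I am highly confident of the wording error; the power figures are conditional on these assumptions.

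**What to change.** In section 8.1, replace the paired t-test sentence with one pre-specified primary analysis. Suggested wording: *The primary analysis compares 6-month VAS between arms by ANCOVA with arm and baseline VAS as covariates, at two-sided alpha 0.05, and reports the adjusted difference with its 95% confidence interval.* Baseline and 6-month VAS are already recorded (sections 5.2.2 and 5.2.4).

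- The minimum valid alternative is an unpaired t-test of the 6-month VAS score. An unadjusted change score should not be the primary variable.
- Make Mann-Whitney a sensitivity analysis and not a switch made after a normality check.
- Use the same between-arm approach for ASES, QuickDASH and deposit size.
- Limit paired t-tests to describing change within each arm.
- Name the same primary test in the Statistical Methodology row of the Protocol Summary.

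The cost is wording edits in two places and a simple regression model, with no new visits, data or patients. Four neighbouring matters are separate and are not needed for this correction: the status and alpha of the radiographic endpoint, the sonographic versus X-ray wording, the primary-endpoint label in section 3.2.2, and the mismatch between 128 and d=0.6.
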